10.8.1.2 SARS-CoV-2 Neutralizing Antibodies

Seroconversion is defined as a fold increase above 1 in SARS-CoV-2 neutralizing antibody titer regardless of the serostatus at baseline. In addition, 2-fold and 4-fold increases will be presented.

10.8.2 Geometric Mean

The SARS-CoV-2 spike RBD protein-specific antibody ELISA and SARS-CoV-2 neutralizing antibody are expressed as GMT [geometric mean of reciprocal duplicate dilutions]. It is assumed that the data is skewed hence the geometric mean (GM) and geometric standard deviation (GSD) will be presented. The GM is calculated as the anti-logarithm of the mean of the log-transformed data. The GSD will be calculated as the anti-logarithm transformation of the standard deviation of the log-transformed data.

10.9 Censoring Rules

Authorized/licensed vaccines are available to some subjects, and based on ethical reasons these subjects can decide whether they would like to receive the authorized/licensed vaccine. To avoid any study bias, subjects who are vaccinated with an authorized/licensed vaccine will be censored for safety and immunogenicity at the first day after receiving the authorized/licensed vaccine. The data collected from the censoring time point forward will be included and flagged in the listings output to identify corresponding data.

The following details are to be followed regarding censoring the day after receiving the authorized/licensed vaccine:

- Times are not relevant as neither authorized/licensed vaccine time nor case start time are collected.
- If authorized/licensed vaccine date is complete then censoring starts at first day after the authorized/licensed vaccine day.
- If authorized/licensed vaccine date is incomplete (only day missing) then censoring starts after this month.
- If authorized/licensed vaccine date is incomplete (month missing, year available) then censoring starts after this year.
- If authorized/licensed vaccine date is completely missing, then no censoring can be made.

As these imputations of incomplete authorized/licensed vaccine dates are not an ideal solution this is only to be considered as a fallback solution in case complete licensed vaccine dates cannot be retrieved and an interim workaround for unclean data during trial conduct.

All incomplete or missing authorized/licensed vaccine dates need to be queried.

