6.1 Amendment #1 to Protocol Version 2.0

Protocol Amendment #1 describes the changes to be implemented into protocol version 2.0 in the context of the pause of Trial CV-NCOV-003.

In line with protocol section 5.2.2 “Pausing of the Trial,” the DSMB convened to review the available CVnCoV data across ongoing trials, and notably the available safety data of the pivotal phase2b/3 trial CV-NCOV-004. The DSMB confirmed a favourable safety profile for CVnCoV. The second Interim Analysis data on efficacy from CV-NCOV-004 suggested age dependent efficacy with inconclusive efficacy data in the group > 60 years of age. In consultation with Investigators, a decision has been taken to stop further enrolment into CV-NCOV-003 and amend the current protocol version 2.0 to clarify that all subjects shall undergo safety and immunogenicity follow-up for 3 months following the last CVnCoV. Due to the change in risk/benefit profile, there is sufficient scientific and medical rationale to support an enrolment halt of all ages with comorbidities and for enrolled subjects to complete study activities, allowing standard of care COVID vaccination procedures to be followed by the Investigators or the subject's primary care physician.

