9.4 Estimands

Based on the Protocol Amendment #1, a subset of endpoints will be presented. See Section 6.1, 6.2, 6.3 and 6.4 and Appendix 4 List of Abbreviated Scope Based on SAP Version 2.0 for additional details.

ENDPOINTS (subject level)	ESTIMANDS (population level)
Primary Safety	

The frequency, intensity, and duration of solicited local AEs on each vaccination day and the following 7 days.
 
The frequency, intensity, duration, and relationship to trial vaccination of solicited systemic AEs on each vaccination day and the following 7 days.
 
The occurrence, intensity and relationship to trial vaccination of unsolicited AEs on each vaccination day and the following 28 days.
 
The occurrence and relationship to trial vaccination of SAEs and AESIs throughout the trial.
	
In subjects who received at least one dose of CVnCoV vaccine and a post baseline vaccine safety assessment is available. Subjects receiving an authorized/licensed COVID-19 vaccine during the course of the trial will be censored at the day after intake. The primary safety will be analyzed with the safety analysis set.
 
The number and percentage of subjects overall and by co-morbidity:
 
Each solicited local AE within 7 days (after each trial vaccination by intensity and overall).
 
Each solicited systemic AE within 7 days after each trial vaccination by intensity, by relationship to trial vaccine and overall.
 
The mean duration in days by group with standard deviation of solicited AEs (within the solicited period, total duration).
 
At least 1 unsolicited AEs, at least 1 grade unsolicited AEs and each unsolicited AEs by SOC/PT occurring within 28 days after each trial vaccination and overall by causal relationship to trial vaccine and overall.
 
At least 1 SAE, or at least 1 AESI to vaccine overall by causal relationship to trial vaccine and overall.

ENDPOINTS (subject level)	ESTIMANDS (population level)
Primary Immunogenicity	

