Appendix 2 Adverse Events of Special Interest for SARS-CoV-2 Vaccines

Current list of AESIs (based on Brighton Collaboration via CEPI's Safety Platform for Emergency vACCines [SPEAC] Project):

Immunological disorders:

- o Anaphylaxis
- o Vasculitides
- o Enhanced disease following immunization
- o Multisystem inflammatory syndrome in children

Respiratory disorders:

- o Acute respiratory distress syndrome
- o COVID-19 disease

Cardiac disorders:

Acute cardiac injury including:

- o Microangiopathy
- o Heart failure and cardiogenic shock
- o Stress cardiomyopathy
- o Coronary artery disease
- o Arrhythmia
- o Myocarditis, pericarditis

Hematological disorders:

- o Thrombocytopenia

Coagulation disorder:

- o Deep vein thrombosis
- o Pulmonary embolus
- o Cerebrovascular stroke
- o Limb ischemia
- o Hemorrhagic disease

Renal disorders:

- o Acute kidney injury

Gastrointestinal disorders

- o Liver injury

Neurological disorders:

- o Generalized convulsion
- o Guillain-Barré Syndrome
- o Acute disseminated encephalomyelitis
- o Anosmia, ageusia
- o Meningoencephalitis

Dermatologic disorder:

- o Chilblain-like lesions
- o Single organ cutaneous vasculitis
- o Erythema multiforme

Other:

- o Serious local/systemic adverse reaction following immunization

** These are generally the conditions one encounters in normal subjects as AESI, but in this trial we use comorbid subjects and some of them may have coronary disease, arrhythmias or myocarditis to start with.

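### Adverse events starting on the day of an authorized COVID-19 vaccine stay, unflagged, in the CVnCoV occurrence tables

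*SAP*

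**What the plan says.** SAP 10.9 sets one cut-off for two kinds of data: subjects given an authorized or licensed vaccine "will be censored for safety and immunogenicity at the first day after receiving the authorized/licensed vaccine". The operational rule repeats it: "If authorized/licensed vaccine date is complete then censoring starts at first day after the authorized/licensed vaccine day". The primary safety estimand in SAP 9.4 states the same cut-off separately: "Subjects receiving an authorized/licensed COVID-19 vaccine during the course of the trial will be censored at the day after intake".

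On timing, 10.9 says: "Times are not relevant as neither authorized/licensed vaccine time nor case start time are collected". On what is marked: "The data collected from the censoring time point forward will be included and flagged in the listings output to identify corresponding data". The stated purpose of the rule is to keep bias out of the study.

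SAP 6.1 explains why such vaccinations are expected. The amendment stops enrolment while "allowing standard of care COVID vaccination procedures to be followed". Appendix 4 plans a table of authorized or licensed vaccination after dose 1 (Table 14.1.7.1).

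For CVnCoV itself, the SAP puts the injection day inside the reaction window; solicited AEs are counted "on each vaccination day and the following 7 days". The AESI list in SAP Appendix 2 includes anaphylaxis and "Serious local/systemic adverse reaction following immunization".

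**The concern.** Censoring is there to keep another product's effects out of the CVnCoV safety tables. A cut-off on the following day leaves in the injection day itself, a day on which the other vaccine can already cause a reaction. The SAP treats the injection day as a reaction day for CVnCoV but does not do so for the other product.

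The trial has one arm, so no control group offsets an extra event. With 129 subjects analysed (SAP 6.3), and fewer in most co-morbidity rows, one or two events can change how a table reads. This matters most for AESIs, where a single anaphylaxis or serious immunization reaction would draw attention.

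**Working it through.** The plan states no figure to reproduce. The check applies the rule to event dates, follows where same-day events go, and then bounds the size.

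**1. The date rule.** Let V be the date of the authorized vaccine, complete and known.

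| Onset | SAP 10.9 and 9.4 | Safety censoring from V |
|---|---|---|
| V − 1 | kept | kept |
| V | kept, not flagged | censored, flagged |
| V + 1 | censored, flagged | censored, flagged |
| V + 2 | censored, flagged | censored, flagged |

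The two rules differ only for onset on V.

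**2. Can the data separate events on V?** No. AE start times may exist, because SAP 10.5 imputes missing ones and SAP 10.7.1 uses date and time to define treatment-emergent events. Those uses relate to CVnCoV. Without the time of the other vaccine, an AE on V cannot be placed before or after it.

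**3. Which same-day events are recorded, and where do they go?**

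- *SAEs and AESIs* are collected throughout the trial (Protocol 4.2.1; SAP 10.7.3 and 10.7.4). They enter the overall summary (Table 14.3.2.1.1), and AESIs also enter Table 14.3.2.26.1.
- *Unsolicited AEs* are collected by diary on the day of each CVnCoV dose and for 28 days after it (SAP 10.7.3). If V falls in that window, they enter Tables 14.3.2.16.1 to 14.3.2.16.3 and 14.3.2.20.1 to 14.3.2.20.3. SAP 12.7.1.1 also summarises all reported AEs, including later ones, and Table 14.3.2.17.1 covers the whole trial.
- *Solicited AEs* are recorded only on the CVnCoV dose days and the following 7 days (SAP 10.7.2). They matter only if V falls in those few days.
- *Related-event rows* depend on the investigator, who is told to consider concomitant vaccination as an alternative cause (Protocol Appendix 9). A same-day event enters those rows only if judged related or, under Protocol 10.3.5.1, if causality is missing.

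**4. Blood samples.** Under the amended schedule no immunogenicity blood is drawn after the first authorized dose (SAP 6.2, Table 2, note j). A sample from day V therefore precedes the other vaccine, and the day-after rule does no harm there.

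**5. Size.** One affected subject is 1/129 = 0.0078, or 0.8 percentage points of the overall set. More generally:

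expected subjects = 129 × u × r,

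where u is the share taking an authorized vaccine in the trial and r is the share of those with a recorded AE on that day. The documents give neither, so the values below are assumptions.

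| u | r | Expected subjects | Points of 129 |
|---|---|---|---|
| 10% | 1% | 129 × 0.10 × 0.01 = 0.13 | 0.1 |
| 30% | 10% | 129 × 0.30 × 0.10 = 3.9 | 3.0 |
| 60% | 30% | 129 × 0.60 × 0.30 = 23.2 | 18.0 |

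The high values of r are hard to reach when most vaccinations fall outside the diary windows in step 3. The range shows only that the documents do not fix the size.

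**The case against.** **Occurrence is not attribution.** A reader might infer that the SAP credits these events to CVnCoV. It does not. The tables count occurrences, and related AEs, SAEs and AESIs have separate rows in the overall summary. This stands, and it limits the effect on the related rows. It does not correct the occurrence tables.

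**Not every same-day AE is captured.** A reader might infer that all reactions to the other vaccine enter. The collection windows prevent that, and subjects planning an authorized vaccine up to 6 weeks after the foreseen second dose were excluded at entry (Protocol 6.2, criterion 4). This stands too. It moves the weight to SAEs, AESIs and the whole-trial tables.

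**No evidence that this is the peak day.** It is tempting to say that the rule keeps the day on which the other vaccine is most likely to cause an event. The documents do not say so. The phrase "on each vaccination day and the following 7 days" concerns the trial vaccine and says nothing about when reactions peak. The point needs only that same-day reactions are possible.

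**Over-counting is the cautious direction, and the listings allow a check.** Without times, either rule misplaces some events. With 129 subjects, the vaccination, censoring and AE listings can be cross-read by date. Both are fair, but a reader of the tables alone would not know that such events are included, and their count would appear nowhere.

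**Conclusion.** The point holds, and it is narrow. SAP 10.9 and 9.4 keep AEs, SAEs and AESIs with onset on the day of the authorized vaccine in the CVnCoV occurrence tables without a flag, contrary to the rule's own aim. This follows from the text and rests on no assumed number.

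The size cannot be computed. Each affected subject adds 0.8 points overall. A reader might take all 129 subjects as exposed, or divide 129 by the seven co-morbidities to get strata of about 18. Neither is supported: 10.9 says that such vaccines are available to only some subjects, no stratum sizes are given, and subjects with several co-morbidities count in several strata (SAP 12.0).

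The analysis is descriptive and no decision rule depends on these counts. This is a cheap improvement.

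**What to change.** Split the rule in SAP 10.9 and make the same change to the primary safety estimand in 9.4. Changing only one would leave the two sections in conflict.

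- For AEs, SAEs and AESIs, start censoring on the day of the authorized or licensed vaccine.
- Flag events with onset on that day in the listings, and give their count in a footnote to each affected table, so that totals with and without them are visible.
- For blood samples, keep the first day after.

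The cost is SAP wording, one derived flag and footnotes; no new data are needed. The downside is small: an AE that began before the injection on that day leaves the main count but stays visible in the listing and footnote.

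The change does not touch the rules for incomplete vaccine dates, which delay censoring to the end of the month or year. SAP 10.9 already calls those a fallback and requires such dates to be queried.

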6.2 Description of changes to Trial CV-NCOV-003 Protocol Version 2.0

Subjects who already received at least 1 CVnCoV dose are requested to remain in the study for 3 months following their last CVnCoV dose for safety and immunogenicity follow-up. Subjects will follow the amended Schedule of Activities (Table 2) until they reach 3 months of follow-up post-CVnCoV last dose. The follow-up period including Visit 9/Day 211 and Phone Contact/Day 302 is removed. The previous End of Trial Visit/Day 393 is amended to 3 months post last injection of CVnCoV as described in Table 1.

Any subjects currently in screening will be considered screen failures and will not receive CVnCoV vaccination in line with the enrolment halt. No additional screenings will be performed.

Subjects will be provided with adequate information about the changes to the study, in accordance with applicable local regulations and in line with protocol section 12.4 "Informed Consent." The original schedule of visit is contained in Protocol version 2.0.

Table 1 Summary of visits to be included in the 3-month follow-up

The last injection of CVnCoV was on:	The subject will perform the study visits as planned in the Schedule of Activities, up to:	The subject will additionally have an end of trial visit ^a at:
Day 1	Day 57	Day 91
Day 29	Day 120 ^b	Day 120 ^b

NA: not applicable

- a) At this visit, the procedures described for the End of Trial in Table 2 should be performed.
- b) As Day 120 will be the end of trial visit, the procedures to be followed are those described for the End of Trial in Table 2.

Table 2 Amended Schedule of Activities

Visit		Safety contact ^a	Phone contact						End of Trial ^c
Trial Day	2 (D1 +1d)	9 (D1 +8d)	15 (D1+ 14d)	29 (D1 +28d)	30 ^b (D29 +1d)	43 (D29 +14d)	57 (D29 +28d)	120 (D29 +91d)	
Visit Window (days)	-0/ +0	-0/ +7	-2/ +4	-3/ +14		-2/ +4	-2/ +4	-2/ +4	
Physical examination ^d									X
Symptom-directed physical examination	X			X	X	X	X		
Vital signs ^d	X			X	X	X	X		X
Diary retraining ^e	X				X	X			
Diary review ^e	X	X		X	X	X	X		
Solicited AEs collected by diary ^e	X	X		X	X				
Unsolicited AEs collected by diary ^e	X	X		X	X	X	X		
SAEs ^f	X	X	X	X	X	X	X	X	X
Intercurrent medical conditions ^f	X	X	X	X	X	X	X	X	X
AESIs ^f	X	X	X	X	X	X	X	X	X
Concomitant medication/vaccination	X	X	X	X	X	X	X	X	X
Safety laboratory (~8 mL) ^g – Up to 50 subjects per co-morbidity	X			X	X	(X) ^h	X	(X) ^h	
Nasopharyngeal swab collection for rapid diagnosis on site and PCR testing ⁱ					(X)				

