9.5.3 Safety Analysis Set (SAS)

The Safety Analysis Set will consist of all subjects who received at least 1 dose of CVnCoV and for whom any post-vaccination safety data are available.

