14.3.2 Adverse Events Data Tables
Table 14.3.2.1.1 Overall Summary of Adverse Events (Safety Analysis Set)
Table 14.3.2.2.1 Summary of Solicited Adverse Events and Maximum Grade Occurring on the Day of Vaccination and the following 7 Days after any Dose (Safety Analysis Set)
Table 14.3.2.3.1 Local Solicited Adverse Events and Maximum Grade Occurring on the Day of Vaccination and the following 7 Days after any Dose (Safety Analysis Set)
Table 14.3.2.4.1 Systemic Solicited Adverse Events and Maximum Grade Occurring on the Day of Vaccination and the following 7 Days after any Dose (Safety Analysis Set)
Table 14.3.2.6.1 Duration of Solicited Adverse Events Occurring on the Day of Vaccination and the following 7 Days after any Dose (Safety Analysis Set)

Table 14.3.2.16.1 Unsolicited Adverse Events by System Organ Class and Preferred Term Occurring on the Day of Vaccination and the following 28 Days after any Dose (Safety Analysis Set)
Table 14.3.2.16.2 Unsolicited Adverse Events by System Organ Class and Preferred Term Occurring on the Day of Vaccination and the following 28 Days after Dose 1 (Safety Analysis Set)
Table 14.3.2.16.3 Unsolicited Adverse Events by System Organ Class and Preferred Term Occurring on the Day of Vaccination and the following 28 Days after Dose 2 (Safety Analysis Set)
Table 14.3.2.17.1 Unsolicited Adverse Events for Duration of Trial by System Organ Class and Preferred Term (Safety Analysis Set)
Table 14.3.2.17.2 Related Unsolicited Adverse Events for Duration of Trial by System Organ Class and Preferred Term (Safety Analysis Set)
Table 14.3.2.20.1 Unsolicited Adverse Events by System Organ Class, Preferred Term, and Maximum Severity Occurring on the Day of Vaccination and the following 28 Days after any Dose (Safety Analysis Set)
Table 14.3.2.20.2 Unsolicited Adverse Events by System Organ Class, Preferred Term, and Maximum Severity Occurring on the Day of Vaccination and the following 28 Days after Dose 1 (Safety Analysis Set)
Table 14.3.2.20.3 Unsolicited Adverse Events by System Organ Class, Preferred Term, and Maximum Severity Occurring on the Day of Vaccination and the following 28 Days after Dose 2 (Safety Analysis Set)
Table 14.3.2.26.1 Adverse Events of Special Interest for Duration of Trial by System Organ Class and Preferred Term (Safety Analysis Set)
Table 14.3.2.29.1 Adverse Events Leading to Study Withdrawal by System Organ Class and Preferred Term (Safety Analysis Set)

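### Trial-long SAE and AESI percentages stop counting at a licensed COVID-19 vaccine but take no account of the shortened follow-up

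*SAP*

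**What the plan says.** SAP 10.9 provides that subjects who take a licensed vaccine (used here for any authorised or licensed COVID-19 vaccine) "will be censored for safety and immunogenicity at the first day after receiving the authorized/licensed vaccine". It then sends the later data to listings: "The data collected from the censoring time point forward will be included and flagged in the listings output to identify corresponding data".

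SAP 9.4 gives the relevant primary safety endpoint as "The occurrence and relationship to trial vaccination of SAEs and AESIs throughout the trial". The summary measure is "The number and percentage of subjects overall and by co-morbidity", and the matching entry reads "At least 1 SAE, or at least 1 AESI to vaccine overall by causal relationship to trial vaccine and overall". The same estimand cell repeats the censoring at licensed vaccination but does not say what risk, over what period, is being estimated.

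The Safety Analysis Set (SAP 9.5.3) is "all subjects who received at least 1 dose of CVnCoV and for whom any post-vaccination safety data are available". It sets no minimum follow-up and does not remove censored subjects.

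In Appendix 4, AESIs have their own table, 14.3.2.26.1, titled "Adverse Events of Special Interest for Duration of Trial by System Organ Class and Preferred Term". SAEs appear as a percentage only as lines of the overall summary, Table 14.3.2.1.1, because SAP 12.7.1.1 marks the SAE tables by SOC and PT as outside the abbreviated scope. Table 14.1.7.1 covers licensed-vaccine use and Listing 16.2.3.3 covers censoring. No safety table mentions person-time, number at risk or a time-to-event estimate.

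**The concern.** Censoring handles shortened follow-up only when the analysis uses time at risk. Combined with a crude percentage, it takes events out of the numerator and leaves the subject in the denominator as though event-free to the end.

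Licensed vaccination during follow-up was foreseeable. The amendment's rationale allows standard-of-care COVID-19 vaccination, and Protocol 10.3.6 already considered that an important share of subjects might opt for it. Entry criterion 4 excludes only planned licensed vaccination up to six weeks after the second dose, which is Day 29 + 42 = Day 71, well short of Day 120.

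The AESI list includes COVID-19, heart failure, coronary artery disease, arrhythmia and stroke. In subjects with these co-morbidities such events can occur at any time, so lost follow-up can mean lost events. If uptake differed between co-morbidity groups, their columns would rest on different lengths of observation and the reader could not see it.

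**Working it through.** The plan states no SAE or AESI risk, no censored share and no bias, so there is no figure of its own to reproduce. The direction follows from logic and the size from assumptions.

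**Direction.** When the vaccine date is complete, the subjects with an event before censoring are a subset of those with an event by the end of the trial. The crude percentage can therefore only equal or fall below the full-period figure, even if the decision to take a licensed vaccine is related to health.

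**Inputs from the documents.** 129 subjects (SAP 6.3). End of trial at Day 120 after two doses (SAP 6.2, Table 1), which is T = 119 days from first dose. Day 71 as the end of the entry restriction on planned licensed vaccination.

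**Assumptions.** Censored share q from 10% to 80%; censoring at Day 43, 71 or 91 (c = 42, 70 or 90 days), since earlier unplanned use is possible; true risk R to Day 120 of 2%, 5% or 10%; constant hazard, with a front-loaded alternative.

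**Formula.** Expected crude proportion = (1 − q) × R + q × F(c), where F(c) = 1 − exp(−H × c/T) and H = −ln(1 − R).

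**Worked case: R = 5%, q = 50%, Day 71.**
- H = −ln(0.95) = 0.0513
- F(70) = 1 − exp(−0.0513 × 70/119) = 0.0297
- Crude = 0.5 × 0.05 + 0.5 × 0.0297 = 0.0399, shown as 3.99%
- Shortfall = 129 × (0.0500 − 0.0399) = 1.3 subjects

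A rough cross-check: mean follow-up is 0.5 × 119 + 0.5 × 70 = 94.5 days, or 79% of 119, and 79% of 5% is about 4.0%.

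If events cluster early (Weibull shape 0.5), c/T is replaced by its square root, 0.767. Then F(70) = 0.0386, the crude figure is 4.43% and the shortfall is 0.7 subject.

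**Range for a true 5% risk, constant hazard** (crude percentage, with subjects missed of 129):

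| Censored share | Day 43 | Day 71 | Day 91 |
|---|---|---|---|
| 10% | 4.68 (0.41) | 4.80 (0.26) | 4.88 (0.15) |
| 30% | 4.04 (1.24) | 4.39 (0.78) | 4.64 (0.46) |
| 50% | 3.40 (2.07) | 3.99 (1.31) | 4.40 (0.77) |
| 80% | 2.44 (3.31) | 3.38 (2.09) | 4.04 (1.23) |

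Relative understatement in this table runs from about 2% to about 51%. Over true risks of 2% to 10%, the shortfall runs from 0.06 to about 6.6 subjects.

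**Does time at risk repair it?** In a simulation with 129 subjects, 20,000 runs and censoring independent of events, both Kaplan-Meier and person-time (converted to a 119-day risk) returned 5.0% in the worked case. With a true 10% risk and the same censoring, both returned about 10.0%, against a crude 8.0%.

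**The case against.** The strongest reply is that censoring is part of the stated estimand, and that SAP 10.9 gives avoidance of bias as its purpose. If the target is events seen before a licensed vaccine, the crude percentage is a valid description. This stands. A reader might infer that the SAE and AESI percentages are simply biased low, but the documents do not support that without a full-period target, which SAP 9.4 never names. What remains is that the alternative target is not stated either, and that the follow-up behind the percentage goes unreported.

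Other limits also stand:

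- The full denominator is a reasonable inference, not a written rule. The table shells are a separate document.
- A reader might take the Day 91 and Day 120 end-of-trial visits as unequal follow-up by design. They are 90 and 91 days after the last dose respectively, so they differ only when counted from the first dose.
- Incomplete vaccine dates delay censoring, and missing ones prevent it. Both push the percentage up, although SAP 10.9 requires such dates to be queried.
- The trial is descriptive and the co-morbidity strata overlap. An even split would give about 129/7 = 18 subjects per group, so differences between columns will be imprecise whatever method is used.
- Post-censoring events stay in the listings, and Listings 16.2.3.3 and 16.2.7.5 let a reader trace censoring and SAEs subject by subject. Listings do not correct the summary percentages.

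It is also tempting to extend the argument to every table described as covering the duration of the trial. That fails for unsolicited AEs. SAP 10.7.3 collects them by diary for 28 days after each dose, so person-time to the end of trial would include time outside routine collection and dilute the rate. Censoring after about Day 57 (Day 29 + 28) costs those tables little.

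**Conclusion.** The point holds for SAEs and AESIs only. Their trial-long percentages combine a numerator cut at licensed vaccination with, on the natural reading, the whole Safety Analysis Set as denominator, and no planned table shows time at risk. They equal or understate full-period risk; as risk before licensed vaccination they are legitimate but rest on unequal, undisclosed follow-up.

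The size cannot be fixed from the documents. It may be a fraction of one subject or several of 129; the middle illustration, about 1.3 subjects, depends on an assumed 50% censored at Day 71, a 5% risk and a constant hazard. Non-comparability between co-morbidities is possible but not shown, since uptake by group is not given. This is an inexpensive improvement to a primary safety summary and does not invalidate the safety analysis.

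**What to change.** 1. In SAP 9.4 (Primary Safety), state that the target for SAEs and AESIs is risk before licensed vaccination, and state the denominator in words.
2. For the SAE and AESI lines of Table 14.3.2.1.1 (all reported AEs) and for Table 14.3.2.26.1, add person-time at risk, overall and by co-morbidity. Count it from first dose to the earlier of censoring or the subject's end of trial, stopping at the first event where the numerator counts subjects. Beside it give the event rate per 100 person-months, or a Kaplan-Meier risk to a stated day. Keep the crude percentage.
3. Do not apply trial-long person-time to Tables 14.3.2.17.1 and 14.3.2.17.2 or to the unsolicited-AE lines of Table 14.3.2.1.1.

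The cost is a few columns built from dates already collected. A rate assumes roughly constant risk over three to four months, which is open to doubt after a vaccine. Kaplan-Meier avoids that but assumes non-informative censoring, and estimates risk as if no licensed vaccine had been given, so it should be labelled that way. By-co-morbidity figures will be imprecise with 129 subjects.

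### For authorized-vaccine dates still incomplete after query, SAP 10.9 keeps safety time known to follow the other vaccine; a year-only 2021 date in effect censors nothing (low priority)

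*SAP*

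**What the plan says.** The primary safety estimand in SAP 9.4 sets the target: "Subjects receiving an authorized/licensed COVID-19 vaccine during the course of the trial will be censored at the day after intake". SAP 10.9 gives the purpose: "To avoid any study bias, subjects who are vaccinated with an authorized/licensed vaccine will be censored for safety and immunogenicity", starting on the first day after receipt.

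For incomplete dates SAP 10.9 has three rules:
- Day missing: "If authorized/licensed vaccine date is incomplete (only day missing) then censoring starts after this month".
- Month missing: "If authorized/licensed vaccine date is incomplete (month missing, year available) then censoring starts after this year".
- Nothing known: "If authorized/licensed vaccine date is completely missing, then no censoring can be made".

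The same section limits their use, since "this is only to be considered as a fallback solution in case complete licensed vaccine dates cannot be retrieved", and requires every incomplete date to be queried. On listings it says: "The data collected from the censoring time point forward will be included and flagged in the listings output to identify corresponding data".

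The amended Schedule of Activities (SAP 6.2, Table 2; same table in the Protocol Amendment) has a row "Concomitant medication/vaccination" marked at every scheduled visit and contact. Nothing in 10.9 uses the contact at which the vaccine was recorded.

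**The concern.** Each fallback takes the latest possible date or none, so its error runs one way: it can only keep time after the other vaccine. Part of that time is not uncertain at all. Once a contact has recorded the authorized vaccine, every later day follows it, whatever day or month is missing. The statement that a fully missing date rules out censoring is therefore not correct when the recording contact is known.

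The SAP applies this logic elsewhere. SAP 10.5 limits imputed AE end dates to the end of the trial, and moves an imputed start date that falls after the resolution date. SAP 10.9 ignores a comparable known bound.

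At stake is whether a late SAE, AESI or other safety finding is counted under CVnCoV follow-up when it is known to come after another vaccine. With 129 subjects spread over seven co-morbidity strata, and subjects counted in more than one, a single event can show in a stratum. Authorized vaccination is foreseen: Protocol 8.1 lists wanting it as a reason for stopping CVnCoV doses.

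**Working it through.** **Inputs**
- Amendment date 27-JUL-2021 (SAP 6.0), taken as the latest possible first dose. This is an assumption; no last first-dose date is given. The amendment makes subjects in screening screen failures, and SAP 6.3 bases the analysis on the 129 enrolled at the pause decision. Both support the assumption but do not state it.
- Day 29 window -3/+14 and Day 120 window -2/+4 (SAP 6.2, Table 2).
- Last visit: Day 120 after two doses, Day 91 after one (SAP 6.2, Table 1).

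**1. Schedule check.** 29 + 91 = Day 120, as the schedule states.

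**2. Latest last visit**
- Two doses, nominal: 27-JUL-2021 + 28 + 91 = 23-NOV-2021.
- Two doses, full windows: 27-JUL-2021 + 28 + 14 = 7-SEP-2021 (dose 2); + 91 + 4 = 11-DEC-2021.
- One dose, nominal Day 91: 27-JUL-2021 + 90 = 25-OCT-2021.

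**3. Year-only 2021 date.** Censoring starts on 1-JAN-2022, after all three dates. Days censored: 0. Flagging starts at the same point, so days flagged: 0.

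**4. How far the assumption can slip.** For an in-window Day 120 to reach 1-JAN-2022, the first dose must be on 1-JAN-2022 - (28 + 14 + 91 + 4) = 1-JAN-2022 - 137 days = 17-AUG-2021, which is 21 days after the amendment.

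**5. Day missing.** Lateness = month length - day of vaccination. In a 31-day month this is 0 to 30 days, mean 15.0 if all days are equally likely.

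**6. What a cap at the recording contact changes (year-only or fully missing date)**

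| Subject | Vaccine first recorded | Days after that contact kept now | With cap |
|---|---|---|---|
| One dose | Day 29 | 91 - 29 = 62 | 0 |
| One dose | Day 57 | 91 - 57 = 34 | 0 |
| Two doses, early receiver | Day 57 | 120 - 57 = 63 | 0 |
| Either | Last visit | 0 | 0 (no effect) |

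Time between the true date and the recording contact remains. For a vaccine recorded at Day 57 but not at Day 43, that is at most 57 - 43 = 14 days at nominal visit dates.

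**7. Where the cap does not help.** Exclusion 4 (Protocol 6.2) covers planned authorized vaccination up to 6 weeks after dose 2: 29 + 42 = Day 71. A two-dose subject vaccinated then has no scheduled visit before Day 120, so up to 120 - 71 = 49 days after the vaccine stay in, unless another contact recorded it.

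**8. Exposed outputs in the abbreviated scope (SAP Appendix 4)**
- Table 14.3.2.1.1, including its SAE, AESI, medically attended and intercurrent-condition lines.
- Duration-of-trial Tables 14.3.2.17.1, 14.3.2.17.2 and 14.3.2.26.1. Appendix 4 includes 14.3.2.17.2, although SAP 12.7.1.1 marks related unsolicited AEs by SOC and PT as out of scope.
- AEs leading to withdrawal, such as Table 14.3.2.29.1.
- Late laboratory and vital-sign results (14.3.3 tables, Table 14.3.4.1).

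Solicited AEs (7 days) and 28-day unsolicited AEs are little affected.

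**The case against.** The strongest reply is that this is an admitted last resort. SAP 10.9 itself calls the imputation less than ideal, every incomplete date is queried, interim analyses are gone (SAP 11.1), and the results are descriptive for an abbreviated report. That limits how often the rule will matter. It does not change what the rule does to a date that stays incomplete.

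Keeping events of uncertain timing is a reasonable safety convention, and that stands. The cap keeps them too; it removes only time known to follow the other vaccine.

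Traceability is partly there. Table 14.1.7.1 and Listings 16.2.3.3 and 16.2.4.5 let a reader find the subjects, and SAP 10.5 generally lists original incomplete data. But their later events carry no flag if censoring never starts. Causality assessment must weigh concomitant vaccination (Protocol Appendix 9), which limits distortion of related-event counts but not of all-event counts.

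Feasibility is a fair challenge. The schedule shows that vaccination is collected at each contact, not that the database stores the contact of first report or a negative answer at each contact.

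A reader might infer more than the documents support:
- That the safety results are materially biased. No count of incomplete dates is given.
- That antibody results are contaminated. Footnote j of the amended schedule stops immunogenicity draws after the first authorized dose, so only a sample drawn despite it would be exposed.
- That the 63-day two-dose case is typical. It needs receipt earlier than exclusions 3 and 4 foresee as planned use.
- That some days would be censored after all. This needs the superseded +30-day window of the Day 393 visit: 7-SEP-2021 + 91 + 30 = 6-JAN-2022, at most 6 days. The amended Day 120 window is -2/+4.

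**Conclusion.** The point holds, at low priority. For dates still incomplete after query, SAP 10.9 keeps time known to follow the authorized vaccine. For a year-only 2021 date it censors and flags nothing within the amended visit windows, provided first doses ended by 27-JUL-2021; the two-dose result survives a slip of up to 20 days in that date.

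The size per affected subject ranges from nothing (first recorded at the last visit) to about two months (62 days for a one-dose subject recorded at Day 29). The size for the trial cannot be stated, since the number affected may be 0 of 129. The gain from a cap falls mainly on one-dose subjects and early receivers.

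**What to change.** In SAP 10.9, for day-missing, year-only and fully missing dates, start censoring at the earlier of the current 10.9 date and the day after the contact at which the authorized vaccine was first recorded. For a fully missing date the contact alone decides. If the database does not hold that contact, use the eCRF entry date. Protocol Appendix 1 (item 10) asks for entry within 5 days of most visits, so this bound is looser by up to 5 days if the deadline is kept.

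Flag listings from the same point, and report the number of subjects with imputed vaccine dates, for example in Table 14.1.7.1.

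An earliest-date sensitivity analysis is optional. It makes sense only if a date stays incomplete and the eCRF shows the last contact without an authorized vaccine. It may drop true CVnCoV follow-up: up to 120 - 57 = 63 days for a two-dose subject first reported at Day 120, or 91 - 57 = 34 days for a one-dose subject first reported at Day 91, at nominal visit dates.

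The cost is a sentence or two in 10.9, one derivation and one reported count. If all dates are retrieved, the results do not change.
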